14 PROTECTION OF HUMAN SUBJECTS

14.1 Privacy

MSK's Privacy Office may allow the use and disclosure of protected health information pursuant to a completed and signed Research Authorization form. The use and disclosure of protected health information will be limited to the individuals described in the Research Authorization form. A Research Authorization form must be completed by the Principal Investigator and approved by the IRB and Privacy Board (IRB/PB).

15 INFORMED CONSENT PROCEDURES

Before protocol-specified procedures are carried out, consenting professionals will explain full details of the protocol and study procedures as well as the risks involved to participants prior to their inclusion in the study. Participants will also be informed that they are free to withdraw from the study at any time. All participants must sign an IRB/PB-approved consent form indicating their consent to participate. This consent form meets the requirements of the Code of Federal Regulations and the Institutional Review Board/Privacy Board of this Center. The consent form will include the following:

1. The nature and objectives, potential risks and benefits of the intended study.
2. The length of study and the likely follow-up required.
3. Alternatives to the proposed study. (This will include available standard and investigational therapies. In addition, patients will be offered an option of supportive care for therapeutic studies.)
4. The name of the investigator(s) responsible for the protocol.
5. The right of the participant to accept or refuse study interventions/interactions and to withdraw from participation at any time.

Before any protocol-specific procedures can be carried out, the consenting professional will fully explain the aspects of patient privacy concerning research specific information. In addition to signing the IRB Informed Consent, all patients must agree to the Research Authorization component of the informed consent form.

Each participant and consenting professional will sign the consent form. The participant must receive a copy of the signed informed consent form.

APPENDIX A – PERFORMANCE STATUS CRITERIA

ECOG Performance Status Scale		Karnofsky Performance Scale	
Grade	Descriptions	Percent	Description
0	Normal activity. Fully active, able to carry on all pre-disease performance without restriction.	100	Normal, no complaints, no evidence of disease.
		90	Able to carry on normal activity; minor signs or symptoms of disease.
1	Symptoms, but ambulatory. Restricted in physically strenuous activity, but ambulatory and able to carry out work of a light or sedentary nature (e.g. , light housework, office work).	80	Normal activity with effort; some signs or symptoms of disease.
		70	Cares for self, unable to carry on normal activity or to do active work.
2	In bed <50% of the time. Ambulatory and capable of all self-care, but unable to carry out any work activities. Up and about more than 50% of waking hours.	60	Requires occasional assistance, but is able to care for most of his/her needs.
		50	Requires considerable assistance and frequent medical care.
3	In bed >50% of the time. Capable of only limited self-care, confined to bed or chair more than 50% of waking hours.	40	Disabled, requires special care and assistance.
		30	Severely disabled, hospitalization indicated. Death not imminent.
4	100% bedridden. Completely disabled. Cannot carry on any self-care. Totally confined to bed or chair.	20	Very sick, hospitalization indicated. Death not imminent.
		10	Moribund, fatal processes progressing rapidly.
5	Dead.	0	Dead.

APPENDIX B – POTENTIAL DRUG-DRUG INTERACTIONS

B.1 Potential CYP-Mediated Interactions

In vitro data indicate that GSK2141795 is a CYP3A4 substrate (GSK2141795 Investigator's Brochure, 2012). Drugs that potently inhibit CYP3A4 could lead to increased GSK2141795 exposure in subjects, and should either be prohibited or used with caution. Drugs which are strong inducers of CYP3A and may result in lower exposures of GSK2141795 should also be prohibited. GSK2141795 also appears to be a moderate *in vitro* inhibitor of CYP2C8 (50% inhibitory concentration [IC₅₀] 3 mcM) and CYP3A4 (IC₅₀ 11 mcM). Drugs that are substrates of CYP3A4 or CYP2C8 with a narrow therapeutic index may be prohibited. Drugs that are sensitive substrates of CYP3A4 or CYP2C8 should be used with caution.

Therefore, drugs that potently inhibit CYP3A4 could lead to increased GSK2141795 exposure in subjects, and drugs which are strong inducers of CYP3A are prohibited (see [Tables](#) below). Furthermore, drugs that are substrates of CYP3A4 or CYP2C8 with a narrow therapeutic index are prohibited (see [Tables](#) below).

Whether or not GSK2141795 is a substrate of hepatic uptake transporter OATP is unknown, therefore co-administration of OATP potent inhibitors should be performed with caution.

Because the lists of these agents are constantly changing, it is important to regularly consult a frequently-updated list such as <http://medicine.iupui.edu/clinpharm/ddis/table.aspx>; medical reference texts such as the Physicians' Desk Reference may also provide this information. As part of the enrollment/informed consent procedures, the patient will be counseled on the risk of interactions with other agents, and what to do if new medications need to be prescribed or if the patient is considering a new over-the-counter medicine or herbal product.

B.2 Oral Steroids

Oral steroids should be used with caution and subjects monitored for steroid-induced hyperglycemia. Short courses (up to a maximum of 14 days) of oral corticosteroids intended to treat study treatment related rash or diarrhea are allowed. Budesonide is recommended for supportive care of diarrhea. Subjects will be instructed to inform the investigator before taking any of these or any other medications. Investigators (or their appropriate designee) will be expected to review concomitant medications with the subject at each clinical visit.

B.3 Herbal and Dietary Supplements

Because the composition, PK, and metabolism of many herbal supplements are unknown, the concurrent use of all herbal supplements is prohibited during the study (including, but not limited to, St. John's wort, kava, ephedra [ma huang], ginkgo biloba, dehydroepiandrosterone [DHEA], yohimbe, saw palmetto, or ginseng). Subjects should abstain from taking any herbal and dietary supplements within 5 half lives (or 14 days if the drug is a potential enzyme inducer) prior to the first dose of either study drug until completion of the follow-up visit, unless in the opinion of the Investigator and sponsor there is little concern for a potential drug-drug interaction with the study

drug(s). For example, specific dietary supplements for evaluable deficiencies or imbalances (e.g. Vitamin D, zinc, omega 3) are not prohibited. The investigator should contact a CTEP Medical Monitor before initiating treatment with any herbal preparation.

B.4 Other Prohibited Medications

Other anti-cancer therapy while on study treatment (note: megestrol [Megace] if used as an appetite stimulant is allowed).

Concurrent treatment with bisphosphonates is permitted; however, treatment must be initiated prior to the first dose of study therapy. Prophylactic use of bisphosphonates in patients without bone disease is not permitted, except for the treatment of osteoporosis.

Use of repaglinide, rosiglitazone and/or pioglitazone is permitted only after consultation with the CTEP Medical Monitor.

B.5 Tables

The following concurrent medications are **prohibited** while patients are receiving study drugs:

Metabolism Class	Therapeutic Area	Agents
CYP3A Substrate	Hypnotics and Sedatives	Cisapride
	Antidepressant, Antipsychotics, Antianxiety Agents	Pimozide
	Antihistamine	Astemizole
Strong CYP3A Inhibitor/Inducer	Antibiotics	Clarithromycin Telithromycin Rifamycin class agents (e.g., rifampin, rifabutin, rifapentine) Troleandomycin
	Antifungals	Itraconazole ketoconazole
	Antidepressants	Nefazodone
	Antivirals	Atazanvir Delaviridine Indinavir Lopinavir Nelfinavir Ritonavir Saquinavir Nevirapine
	Anticonvulsants	Carbamazepine Phenobarbital Phenytoin
BCRP Substrates	HMG-CoA Reductase Inhibitors, gastrointestinal agents	Rosuvastatin Sulfasalazine

The following concurrent medications (including, but not limited to) should be administered with caution while patients are receiving study drugs:

Metabolism Class	Therapeutic Area	Agents	
CYP3A Inhibitors	Antivirals	Amprenavir Fosamprenavir	
	Antibiotics	Erythromycin	
	Antifungals	Fluconazole Voriconazole	
	Calcium Channel Blockers	Mibefradil Diltiazem Verapamil	
	Miscellaneous	Aprepitant	
	Antibiotics	Erythromycin	
	Antifungals	Fluconazole Voriconazole	
	Calcium Channel Blockers	Mibefradil Diltiazem Verapamil	
CYP3A Inducers	Antivirals	Efavirenz	
CYP2C8 Substrates	HMG CoA-reductase inhibitors	Cerivastatin	
	Thiazolidinediones	Rosiglitazone Pioglitazone	
	Miscellaneous	Chloroquine Zopiclone Repaglinide	

The following additional concurrent medications (including, but not limited to) should be administered with caution while patients are receiving study drugs:

Drugs Potentially Affecting GSK2141795 concentrations	
Drug	Therapeutic Area
quinidine, diltiazem, verapamil	Antiarrhythmics
fluvoxamine, fluoxetine, paroxetine, nefazodone	Antidepressants
aprepitant, cimetidine	Antiemetics
fluconazole, terbinafine, voriconazole	Antifungals
ciprofloxacin, erythromycin, isoniazid	Anti-infectives
mibefradil, diltiazem, verapamil	Calcium Channel Blockers
aprepitant, oxandrolone, tizanidine, gemfibrozil	Miscellaneous
Drugs that may inhibit P-gp and BCRP	
Drug	Therapeutic Area
valsopoda	Miscellaneous
atorvastatin	HMG-CoA Reductase Inhibitors
carvedilol	Congestive Heart Failure

methadone	Analgesic
meperidine	Narcotic
omeprazole	Proton Pump Inhibitor
Drugs that may have their concentrations altered by trametinib or GSK2141795	
repaglinide, rosiglitazone, pioglitazone	Antidiabetics
alfentanil, fentanyl	Analgesics
quinidine	Antiarrhythmics
cilostazol	Anticoagulants and Antiplatelets
astemizole	Antihistamines
diergotamine, ergotamine, eletriptan	Antimigraine agents
pimozide	Antipsychotics
buspirone	Anxiolytics
felodipine	Calcium Channel Blockers
sildenafil, tadalafil, vardenafil	Erectile Dysfunction agents
cerivastatin, ovastatin, simvastatin, atorvastatin	HMG-CoA Reductase Inhibitors
alprazolam, diazepam, midazolam, triazolam	Hypnotics and Sedatives
cyclosporine, sirolimus, tacrolimus	Immunosuppressive agents
cisapride	Prokinetic agents
cyclosporine, tosemide, chloroquine, zopiclone	Miscellaneous
eplerenone	Selective Aldosterone Blockers
chloroquine, zopiclone	Thiazolidinediones

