8.1.3 GSK2141795 (NSC 767034)

Chemical Name: N-[(1S)-2-amino-1-[(3,4-difluorophenyl)methyl]ethyl]-5-chloro-4-(4-chloro-1-methyl-1H-pyrazol-5-yl)-2-furancarboxamide

Other Names: GSK2141795C

Classification: pan-AKT inhibitor

CAS Registry Number: 1047634-65-0

Molecular Formula: C₁₈H₁₆Cl₂F₂N₄O₂ **M.W.:** 429.25 g/mol

Approximate Solubility: Very slightly soluble in water at room temperature (0.18 mg/mL). Solubility decreases as pH increases; for example solubility in gastric fluid at 37° C is >11

mg/mL.

Mode of Action: GSK2141795 is an ATP competitive pan-AKT inhibitor. AKT, a serine/threonine protein kinase with three isoforms, is active in several pathways that regulate survival, proliferation, tissue invasion and metabolism. Since AKT-mediated pathways are important in tumor proliferation and survival, AKT kinases are promising targets for therapeutic intervention. Hyperactivation of the AKT pathway can also correlate with chemotherapy resistance and poorer prognosis.

Description: white to off-white powder

How Supplied: GSK2141795 capsules are supplied by GlaxoSmithKline and distributed by the DCTD, NCI. The 25 mg capsule is a size 2 Swedish orange opaque body and Swedish orange opaque cap with no markings. The capsule contains active pharmaceutical ingredient, microcrystalline cellulose, and magnesium stearate. The capsules are packaged in white high density polyethylene (HDPE) bottles with white plastic, induction-seal, child-resistant caps. Each bottle contains 35 capsules.

GSK does not have stability data to support repackaging GSK2141795 capsules. Capsules must be dispensed in the original container.

Storage: Store bottles at 2-8° C (36-46° F).

Stability: Shelf life studies of GSK2141795 are on-going.

Route of Administration: Oral administration. Capsules must be taken fasting 1 hour before or 2 hours after a meal.

Potential Drug Interactions: *In vitro* data suggest GSK2141795 is a substrate of CYP450 3A4. Potent inhibitors and inducers of 3A4 are prohibited. GSK2141795 appears to be a moderate inhibitor of CYP 2C8 and 3A4 by *in vitro* testing. Drugs that are substrates of these isoenzymes should be used with caution and ones with a narrow therapeutic index should be avoided.

GSK2141795 is a substrate of p-glycoprotein (P-gp) and breast cancer resistant protein (BCRP). It is also an inhibitor of BCRP and OATP1B1. Administration of sensitive BCRP substrates should be prohibited, such as topotecan.

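### Appendix B.5 lists cisapride, pimozide, astemizole and nefazodone both as prohibited and as drugs to give with caution, and nothing says which table governs

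*Combined protocol and SAP*

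**What the plan says.** Appendix B.5 has three tables of concurrent medications.

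- The first lists drugs that "are prohibited while patients are receiving study drugs". It names cisapride, pimozide and astemizole as CYP3A substrates, and nefazodone among the strong CYP3A inhibitors/inducers.
- The second lists drugs to be given with caution. None of the four is in it.
- The third is headed "The following additional concurrent medications (including, but not limited to) should be administered with caution while patients are receiving study drugs". One row reads "fluvoxamine, fluoxetine, paroxetine, nefazodone". Astemizole, pimozide and cisapride appear lower down, under "Drugs that may have their concentrations altered by trametinib or GSK2141795".

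Two other places bear on potent CYP3A4 inhibitors. Section 8.1.3 is categorical: "Potent inhibitors and inducers of 3A4 are prohibited". Appendix B.1 is not. Its first paragraph says such drugs "should either be prohibited or used with caution". Its second paragraph says "drugs that potently inhibit CYP3A4 could lead to increased GSK2141795 exposure in subjects, and drugs which are strong inducers of CYP3A are prohibited", where the verb of prohibition attaches only to the inducers.

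Exclusion criterion 3.2.7 bars current users of a prohibited medication and refers to Appendix B for the list.

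**The concern.** The first and third tables cover the same patients over the same period and tell the investigator opposite things about four drugs. One of the two instructions must be wrong.

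These are working lists. Under Appendix B.2 investigators "will be expected to review concomitant medications with the subject at each clinical visit", so the tables will be consulted whenever a patient's medication changes. Someone who reaches the third table first will read that the drug may be given with care. Cisapride shows how this can happen: the first table files it under hypnotics and sedatives, the third under prokinetic agents. A search by the prokinetic class finds only the caution entry. (Those row labels may have been disturbed when the PDF was converted to text; the double listing was not.)

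What is at stake is the safety of on-study co-administration. Eligibility is not in dispute, because criterion 3.2.7 turns on prohibition and, read strictly, excludes users of all four drugs. The B.4 condition on repaglinide, rosiglitazone and pioglitazone (consult the CTEP Medical Monitor first) is compatible with a caution listing and is not part of this point.

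**Working it through.** No figure in the plan needs reproducing. The check compares the lists and then looks for a rule that reconciles them.

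**1. Size of the prohibited table.** Counting rifampin, rifabutin and rifapentine separately: 3 CYP3A substrates + 20 strong CYP3A inhibitors/inducers + 2 BCRP substrates = 25 agents.

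**2. Overlap with the caution tables.**

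| Class in the prohibited table | Agents | Also in second table | Also in third table |
|---|---|---|---|
| CYP3A substrates | 3 | 0 | 3 (cisapride, pimozide, astemizole) |
| Strong CYP3A inhibitors/inducers | 20 | 0 | 1 (nefazodone) |
| BCRP substrates | 2 | 0 | 0 |
| Total | 25 | 0 | 4 |

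The overlap is 4/25 = 16%. In the CYP3A-substrate class it is 3/3, so every drug there carries a contrary listing.

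**3. Search for a precedence rule.** None was found in Appendix B or in Sections 3.2.7, 5.2 and 8.1. The protocol does write tie-breakers elsewhere: Section 6 takes the lowest dose level when dose-adjustment recommendations conflict, and Section 7.1 takes the lower grade when an event is on two expedited-reporting exception lists. Neither covers concomitant drugs.

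**4. Does the word *additional* in the third heading settle it?** No. The third table also repeats drugs from the second (diltiazem, verapamil, erythromycin, fluconazole, voriconazole, aprepitant), so it is not confined to new entries.

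**5. Comparison with Section 8.1.3.** Nefazodone is a strong CYP3A inhibitor/inducer by the protocol's own classification, and 8.1.3 prohibits potent 3A4 inhibitors and inducers. Its caution entry therefore conflicts with 8.1.3 as well as with the first table. For the three substrates, 8.1.3 asks for caution, or avoidance where the therapeutic index is narrow. The documents do not state their index, so no contradiction with 8.1.3 is claimed for them.

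**6. Exposure window.** Sections 4.4 and 5.1 close Arm B and crossover to new patients as of 11/06/2015. Section 5.1 ends GSK2141795 supply on March 31, 2017. The latest version is dated 12/01/2016. From then to the end of supply: 30 (December) + 31 + 28 + 31 = 120 days, and 120/7 = 17.1 weeks.

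**The case against.** The double listing is not contestable. The best contrary case is that the rest of the text already points to prohibition.

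- B.1 goes on to say that CYP3A4 or CYP2C8 substrates with a narrow therapeutic index are prohibited and refers to the tables. The only CYP3A-substrate class in the prohibited table is cisapride, pimozide and astemizole, so that table is the natural referent. For nefazodone, two prohibitions stand against one caution entry. This has force, and it is why the correction should keep the ban. But the B.1 sentence names no drug and points to the tables in general. It lets a careful reader infer an answer; it is not a precedence rule.
- A caution entry does not cancel an explicit ban. Agreed, and many sites would follow the stricter list. A safety list should not depend on that.
- Section 5.2 requires all concurrent drugs to be recorded and the local Principal Investigator to be alerted to agents affecting selected CYP450 isoenzymes, and B.2 has patients ask before taking other medication. These safeguards bring the drug to the investigator's notice, but the investigator then turns to the same conflicting tables.
- The practical effect is small. Section 8.1.1 says trametinib is not a CYP substrate *in vitro* and anticipates no interaction with sensitive 3A4 substrates, so patients on GSK2141795 are the ones who matter. Section 12.1.2 gives sites up to 90 days to approve a non-expedited amendment, which could leave only 120 − 90 = 30 days of the window. This stands and limits the severity.
- Rewording B.1 might widen the exclusion in 3.2.7. It need not: 8.1.3 already prohibits potent inhibitors, and B.5 separates the strong class from the CYP3A inhibitors in its second table. The rewording should be tied to the strong class.
- Appendix D was not available to this review, so a rule there cannot be ruled out. Section 5.2 describes it as a patient information sheet.

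**Conclusion.** The concern holds, as a minor point. Four of 25 prohibited agents, including all three prohibited CYP3A substrates, are also listed as drugs to be given with caution, and the text reviewed has no rule to resolve it. Nefazodone's caution entry also contradicts Section 8.1.3. The consequence is confined to concomitant-medication safety, chiefly for patients still on GSK2141795 during the roughly 17 weeks between the latest version and the end of supply. The documents do not show how many patients that is, or whether any took one of these drugs. Eligibility, randomisation, power, PFS and the analysis are untouched. The conclusion assumes that Appendix D contains no precedence rule.

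**What to change.** Delete cisapride, pimozide, astemizole and nefazodone from the third B.5 table, or state above the two caution tables that the prohibited table governs where a drug is in both. Do not resolve it the other way: taking nefazodone out of the prohibited table would conflict with Section 8.1.3.

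Reword B.1 to say that potent CYP3A4 inhibitors, meaning the strong class in the first B.5 table, are prohibited, in line with 8.1.3. As an option, cross-refer to the B.4 consultation condition beside repaglinide, rosiglitazone and pioglitazone.

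The cost is four deleted names (or one added sentence) and one reworded sentence in the next amendment. No eligibility criterion, patient number or study procedure changes.

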APPENDIX C – NEW YORK HEART ASSOCIATION CLASSIFICATIONS

**Clinical Evaluation of Functional Capacity of Patients
with Heart Disease in Relation to Ordinary Physical Activity**

Class	Cardiac Symptoms	Limitations	Need for Additional Rest*	Physical Ability to work**
I	None	None	None	Full time
II	Only moderate	Slight	Usually only slight or occasional	Usually full time
III	Defined, with less than ordinary activity	Marked	Usually moderate	Usually part time
IV	May be present even at rest, and any activity increases discomfort	Extreme	Marked	Unable to work

* To control or relieve symptoms, as determined by the patient, rather than as advised by the physician.

** At accustomed occupation or usual tasks.

Reference: Bruce, R. A.: Mod. Concepts Cardiovasc. Dis. 25:321, 1956.
(Modified from New York Heart Association, 1953).

APPENDIX E – CTEP MULTICENTER GUIDELINES

If an institution wishes to collaborate with other participating institutions in performing a CTEP sponsored research protocol, then the following guidelines must be followed.

Responsibility of the Protocol Chair

- The Protocol Chair will be the single liaison with the CTEP Protocol and Information Office (PIO). The Protocol Chair is responsible for the coordination, development, submission, and approval of the protocol as well as its subsequent amendments. The protocol must not be rewritten or modified by anyone other than the Protocol Chair. There will be only one version of the protocol, and each participating institution will use that document. The Protocol Chair is responsible for assuring that all participating institutions are using the correct version of the protocol.
- The Protocol Chair is responsible for the overall conduct of the study at all participating institutions and for monitoring its progress. All reporting requirements to CTEP are the responsibility of the Protocol Chair.
- The Protocol Chair is responsible for the timely review of Adverse Events (AE) to assure safety of the patients.
- The Protocol Chair will be responsible for the review of and timely submission of data for study analysis.

Responsibilities of the Coordinating Center

- Each participating institution will have an appropriate assurance on file with the Office for Human Research Protection (OHRP), NIH. The Coordinating Center is responsible for assuring that each participating institution has an OHRP assurance and must maintain copies of IRB approvals from each participating site.
- Prior to the activation of the protocol at each participating institution, an OHRP form 310 (documentation of IRB approval) must be submitted to the CTEP PIO.
- The Coordinating Center is responsible for central patient registration. The Coordinating Center is responsible for assuring that IRB approval has been obtained at each participating site prior to the first patient registration from that site.
- The Coordinating Center is responsible for the preparation of all submitted data for review by the Protocol Chair.
- The Coordinating Center will maintain documentation of AE reports. There are two options for AE reporting: (1) participating institutions may report directly to CTEP with a copy to the Coordinating Center, or (2) participating institutions report to the Coordinating Center who in turn report to CTEP. The Coordinating Center will submit AE reports to the Protocol Chair for timely review.
- Audits may be accomplished in one of two ways: (1) source documents and research records for selected patients are brought from participating sites to the Coordinating Center for audit, or (2) selected patient records may be audited on-site at participating sites. If the NCI chooses to have an audit at the Coordinating Center, then the Coordinating Center is responsible for having all source documents, research records, all IRB approval documents, NCI Drug Accountability Record forms, patient registration lists, response assessments scans, x-rays, etc. available for the audit.

Inclusion of Multicenter Guidelines in the Protocol

- The protocol must include the following minimum information:
 - The title page must include the name and address of each participating institution and the name, telephone number and e-mail address of the responsible investigator at each participating institution.
 - The Coordinating Center must be designated on the title page.
 - Central registration of patients is required. The procedures for registration must be stated in the protocol.
 - Data collection forms should be of a common format. Sample forms should be submitted with the protocol. The frequency and timing of data submission forms to the Coordinating Center should be stated.
 - Describe how AEs will be reported from the participating institutions, either directly to CTEP or through the Coordinating Center.
 - Describe how Safety Reports and Action Letters from CTEP will be distributed to participating institutions.

Agent Ordering

- Except in very unusual circumstances, each participating institution will order DCTD-supplied investigational agents directly from CTEP. Investigational agents may be ordered by a participating site only after the initial IRB approval for the site has been forwarded by the Coordinating Center to the CTEP PIO.

